3.1. General Overview

The GAME PAD study is a two-arm randomized controlled trial aimed at evaluating whether a home-based walking program with automated coaching augmented with gamification and behavioral economic principles improves functional capacity in patients with PAD. The study will randomize 100 patients with PAD to a 16-week home-based walking program using goal-setting alone (attention control) or to the same home-based walking program with automated coaching augmented with gamification and behavioral economic principles. There will be a 2-week run-in period to obtain baseline measures of physical activity, followed by a 16-week intervention period, and an 8-week follow-up period (see study protocol figure below).

The study will be conducted using Way to Health, a research information technology platform at the University of Pennsylvania used previously for physical activity behavioral interventions.

After institutional review board (IRB) approval of the study, patients who meet the eligibility criteria will be contacted by email, phone call or letter to invite them to participate. Those who

qualify and express interest will provide online informed consent to the study procedures. All patients will receive a wearable activity tracker (Fitbit Inspire) that will be enrolled in the Way to Health platform. The Fitbit and Way to Health platform will continuously track patients' steps and survey patients regarding pain with walking monthly. Within the Way to Health platform, patients will be randomized to one home-based exercise program or the other. All other management decisions are completely at the discretion of the care providers. Data capture will include:

- **Baseline case report form** (for each patient) collecting clinical information abstracted from the medical record
- **Patient-reported quality of life and functional limitation related to PAD** collected via telephone survey and/or the Way to Health platform at the time of enrollment and at 16- and 24-week follow-up
- **Psychometric features** collected via in-person survey at the time of enrollment
- **Daily step count** and calculated **exercise minutes** collected via FitBit charge
- **Patient-reported pain with ambulation** collected via the Way to Health platform at monthly intervals

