5.1 Primary and secondary outcome measures

The study's primary outcome measure will be change in daily step count from baseline to the intervention period for patients in the intervention arm versus patients in the attention control arm.

Secondary outcome measures will include:

- 1) Change in daily step count from baseline to the follow-up period
- 2) Change in daily number of minutes engaged in light, moderate, or vigorous physical activity from baseline to the intervention period, and from baseline to the follow-up period
- 3) Change in daily number of minutes engaged in moderate, or vigorous physical activity from baseline to the intervention period, and from baseline to the follow-up period
- 4) Change in Walking Impairment Questionnaire score from baseline to the end of the intervention period, and from baseline to the end of the follow-up period
- 5) Change in PROMIS mobility, pain interference, and satisfaction with social roles and activities scores from baseline to the end of the intervention period, and from baseline to the end of the follow-up period
- 6) Change in SF-36 physical functioning scale from baseline to the end of the intervention period, and from baseline to the end of the follow-up period

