regression models to evaluate changes in physical activity outcomes measures adjusting for each participant's baseline step, time at the observation level using calendar month fixed effects, participant random effects, and adjusting for repeated observations of participant step counts. We will compare changes in daily step count and physical activity from baseline to the intervention period, excluding weeks 1-4 (the ramp-up period). We will repeat these analyses, comparing changes in daily step count and physical activity from baseline to the follow-up period. Secondary analyses will fit mixed effects regression models adjusted for other variables of interest such as participant characteristics. Exploratory analyses will fit mixed effects regression models to evaluate associations of participant characteristics or behaviors with strong or poor performance in the outcome measures. In a subgroup analysis, we will separately analyze subgroups reporting and not reporting exertional lower extremity symptoms.

For changes in survey measure scores from baseline to the end of the intervention, and from baseline to the end of follow-up, we will compare the intervention and control arms using paired t-tests, without adjustment for baseline characteristics.

6. Human Research Protection

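### The activity-minute models adjust for baseline steps, not baseline minutes, at a modest cost in precision and with imperfect handling of chance imbalance in the outcome's own baseline

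*Combined protocol and SAP*

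**What the plan says.** Section 5.1 lists two activity-minute outcomes among the secondary measures. One covers light, moderate or vigorous activity. The other is "Change in daily number of minutes engaged in moderate, or vigorous physical activity from baseline to the intervention period". Each is also assessed from baseline to the follow-up period, which makes four comparisons.

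Section 5.3 describes a single mixed-effects model for evaluating "changes in physical activity outcomes measures adjusting for each participant's baseline step". Its other terms are fixed effects for calendar month, participant random effects, and a provision for "adjusting for repeated observations of participant step counts". The plan applies this model to steps and to physical activity over the intervention period without the four ramp-up weeks, and then adds: "We will repeat these analyses, comparing changes in daily step count and physical activity from baseline to the follow-up period".

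No section enters baseline minutes in a model. Further covariates appear only later and are not listed: "Secondary analyses will fit mixed effects regression models adjusted for other variables of interest such as participant characteristics".

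The data should exist. Section 3.1 says "There will be a 2-week run-in period to obtain baseline measures of physical activity", and the same section lists exercise minutes among the data captured by the tracker. Section 4.3, however, describes how to estimate a baseline value for step count only. Section 4.4 stratifies on baseline step count only.

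**The concern.** The baseline of the outcome itself is usually the strongest available predictor of its later value. Daily minutes at a given intensity are not the same quantity as total steps, so baseline steps can stand in for baseline minutes only in part. If baseline minutes are left out, residual variation that the model could have explained stays in the standard error. A chance difference between arms in baseline minutes also feeds into the estimated effect. With 50 patients per arm, and with stratification on steps rather than minutes, such a difference is to be expected.

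At stake are the precision of four listed secondary comparisons and the way their estimates respond to chance imbalance. A programmer who follows the text as written would fit the weaker covariate, although the better one is already needed to compute the change from baseline.

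**Working it through.** **The plan's own figure.** Section 5.2 states 80% power for an 1100-step difference with 50 per arm. With an SD of 2000 in both arms, the standard error is 2000 × √(2/50) = 400. Then 1100/400 = 2.75, and two-sided power is Φ(2.75 − 1.96) = 78.5%, close to the stated value. With both quoted SDs (2000 and 2400, root mean square 2209) two-sided power is 70.2%; that is a separate matter. The figure concerns steps. The plan gives no power, SD or correlation for minutes, so what follows rests on assumptions.

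**Set-up.** Let B be baseline minutes, Y post-baseline minutes (a period average) and S baseline steps. Assume:
- equal variances of B and Y, set to 1;
- r = corr(B, Y), from 0.5 to 0.8;
- q = corr(B, S), from 0.5 to 0.9;
- steps predict later minutes only through baseline minutes, so corr(S, Y) = qr.

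**Residual variances.**
- Own-baseline adjustment, with or without S: 1 − r².
- Change score adjusted for S only: 2(1 − r) − q²(1 − r)², which equals (1 − r²) + (1 − r)²(1 − q²).
- Daily value adjusted for S only: 1 − q²r², which equals (1 − r²) + r²(1 − q²).

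The second term in each of the last two lines is the price of omitting B.

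**Variance ratio against own-baseline adjustment (change score / daily value).**

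| r | q = 0.5 | q = 0.7 | q = 0.8 | q = 0.9 |
|---|---|---|---|---|
| 0.5 | 1.25 / 1.25 | 1.17 / 1.17 | 1.12 / 1.12 | 1.06 / 1.06 |
| 0.6 | 1.19 / 1.42 | 1.13 / 1.29 | 1.09 / 1.20 | 1.05 / 1.11 |
| 0.7 | 1.13 / 1.72 | 1.09 / 1.49 | 1.06 / 1.35 | 1.03 / 1.18 |
| 0.8 | 1.08 / 2.33 | 1.06 / 1.91 | 1.04 / 1.64 | 1.02 / 1.34 |

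The extremes for the change score are:
- r = 0.5, q = 0.5: 0.9375/0.75 = 1.25, and √1.25 = 1.12;
- r = 0.8, q = 0.9: 0.3676/0.36 = 1.02, and √1.02 = 1.01.

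The two responses lose the same at r = 0.5. Above that, the daily value loses more, because r² exceeds (1 − r)².

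**Power.** Take a comparison with 80% power under own-baseline adjustment. Its power with ratio V is Φ(2.8016/√V − 1.96). This gives about 71-79% for the change score and about 45-78% for the daily value.

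**Chance imbalance.** With 50 per arm, the standard error of the arm difference in baseline minutes is √(2/50) = 0.20 SD. After conditioning on steps it is 0.20 × √(1 − q²), which is 0.17 SD at q = 0.5 and 0.09 SD at q = 0.9. Each 1 SD of remaining imbalance moves the estimate by:
- r − 1, or −0.5 to −0.2 SD, for the change score. The subtraction over-corrects, because of regression to the mean.
- r, or +0.5 to +0.8 SD, for the daily value. The imbalance is corrected only through steps.

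A one-standard-error imbalance therefore moves the estimate by about 0.02-0.09 SD (change) or 0.04-0.14 SD (daily value).

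**The case against.** The strongest reply is that the sentence was written for steps and only loosely extended. It opens as the primary analysis, the primary outcome is steps, and its repeated-measures clause mentions step counts alone. For steps the covariate is the right one. This is plausible, but the text then applies the model to physical activity in both periods and gives no other specification. The likely drafting history lowers the severity and leaves the instruction as it stands.

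A reader might infer that imbalance in baseline minutes goes wholly uncorrected. The documents do not support that. Section 5.1 defines these outcomes as changes from baseline, so baseline minutes are subtracted, and the fault is then over-correction. Even if daily values are modelled, baseline steps are a correlated covariate and also the stratification factor, so they remove part of the imbalance.

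A reader might also infer that the minute estimates are biased. Under 1:1 randomisation, adjusting for steps leaves the comparison unbiased on average. The shifts computed above are conditional on the imbalance that happens to occur.

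It is also fair to say that the size rests wholly on assumed correlations and may be negligible. The follow-up value averages many days, so a high r is plausible. At r = 0.8 and q = 0.9, a change-score analysis loses only 2% in variance. That stands, and it is why the size is given as a range that includes this end.

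Finally, Section 5.3 does plan further covariate-adjusted models. They are secondary and their covariates are unnamed, so they do not supply the missing term.

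**Conclusion.** The point holds as a minor one. As written, the four activity-minute comparisons omit their own baseline. Under the stated assumptions (equal variances, r of 0.5-0.8, q of 0.5-0.9, steps informative only through minutes), a change-score analysis carries about 2-25% more variance, and its standard error is about 1-12% larger. If the response is the daily value, the variance is about 6-133% larger (ratios 1.06-2.33). The plan does not say which response is meant, so the size cannot be narrowed further from the documents.

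The issue concerns efficiency and conditional imbalance in secondary outcomes. The primary step analysis is unaffected, and the plan makes no power claim for minutes that this would contradict.

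**What to change.** In Section 5.3, state that:
- each physical activity model adjusts for the baseline value of the outcome being analysed: baseline minutes in the same intensity category for each minute outcome, and baseline steps for steps;
- baseline step count or step stratum stays in the minute models as an additional covariate, since randomisation was stratified on it;
- baseline minutes are computed from the same run-in days that Section 4.3 uses for baseline steps;
- the response is either the change from baseline or the daily value, named explicitly.

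The cost is a few lines of wording. It needs no new data, patients or procedures, because baseline minutes are already required to form the change from baseline. The wording should be settled before unblinded data are examined, so that the covariate is not chosen after the results are known.

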3.2. Site

GAME PAD will enroll patients from the University of Pennsylvania Health System, which consists of five large hospitals including the Hospital of the University of Pennsylvania, Penn Presbyterian Medical Center, Pennsylvania Hospital, and Chester County Hospital, and from Cardiovascular Solutions of Central Mississippi, a private cardiovascular practice primarily serving a socioeconomically depressed region. Regardless of site, all patients will be consented and trial participation will be managed virtually through the Way to Health platform by study staff from the University of Pennsylvania, and no clinical personnel from any site will participate in research procedures or have access to any participant data.

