4.4. Randomization

Participants that have established baseline measures and finished goal selection will be randomly assigned to attention control or the automated coaching + gamification intervention using a 1:1 allocation and stratifying on baseline step count (< 2500 steps, 2500 – 5000 steps, > 5000 steps)

with block randomization and block sizes of 2 using an electronic number generator through the Way to Health research technology platform.

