5.2. Sample Size

Patients with PAD walk approximately 3900 steps/day (SD 2689 steps).¹⁶ With a home-based exercise program, the mean change in steps/day over 4.5 months for patients with PAD was a decrease by 200 steps (SD ~2000 steps).¹⁶ By contrast, a gamification intervention similar to the one proposed increased step count by > 900 steps/day (SD ~2400 steps).¹⁹ With 100 patients (50 in each arm), the study will have 80% power to detect an 1100 step difference in change in daily step count between the two arms with alpha set at 0.05

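### Recruiting site is neither a stratification factor nor a term in the primary model; prespecifying it would cost almost nothing and gain a little precision

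*Combined protocol and SAP*

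**What the plan says.** All places are in the combined protocol and SAP.

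- Section 3.2 names two recruitment sources: a university health system with five large hospitals, and "a private cardiovascular practice primarily serving a socioeconomically depressed region". It also says that consent and participation are handled virtually by one central team, whatever the source, and that clinical staff at the sites take no part in research procedures.
- Section 4.4 randomizes 1:1 in blocks of two, "stratifying on baseline step count" in three bands. There is no other factor.
- Section 5.3 gives the terms of the primary mixed model: baseline steps, "time at the observation level using calendar month fixed effects, participant random effects" and an allowance for repeated observations. Site is not among them. Secondary models are to adjust for further variables, with participant characteristics as the example; site is not named there either.
- Section 5.3 imputes missing days and days under 1,000 steps five times, without listing the predictors.

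**The concern.** The protocol itself describes the practice's population as socioeconomically distinctive, and source is known for every patient at entry. If patients from the two sources change their step counts differently for reasons that baseline steps do not capture, none of the planned terms takes this up. Baseline steps describe the starting level, while the outcome is change. The calendar-month effects are common to both sources, so they do not represent a constant difference between them. The participant random effects have mean zero, so a site difference simply widens their variance.

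Two things follow. The standard error is a little larger than it need be. And in the one trial that is run, if the arms happen to differ in the share of practice patients, the estimate moves by that difference in share times the site difference. These are two views of the same loss of precision, and must not be added together.

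**Working it through.** **The plan's own figure.** Section 5.2 claims 80% power at 50 per arm. The target is a "1100 step difference in change in daily step count between the two arms"; alpha is 0.05, sidedness not stated. It cites SDs of change of about 2,000 (home-based exercise) and 2,400 (gamification).

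- Standard error = SD × √(2/50). SD 2,000 gives 400. The root mean square of the two SDs, √((2,000² + 2,400²)/2) = 2,209, gives 442.
- Two-sided power by normal approximation = Φ(1,100/SE − 1.96). SD 2,000: Φ(2.75 − 1.96) = 78.5%, close to the stated 80%. SD 2,209: Φ(2.49 − 1.96) = 70.2%.

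The stated power is thus reproduced two-sided with the smaller SD. I carry both SDs forward; which one is right is a separate matter.

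**Assumed inputs.** The documents give neither the share of patients from the practice (q) nor a site difference in step change after baseline adjustment (D). I take q = 10% to 50% and D = 250 to 1,000 steps/day. I also use the SDs of change from section 5.2 as residual SDs.

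**Chance imbalance.** With 100q practice patients split at random between two arms of 50, the SD of the between-arm difference in share is 2√(q(1 − q)/99). The shift in the estimate is that difference times D. The percentiles come from the hypergeometric distribution.

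**Precision gain.** The share of variance explained by site is R² = q(1 − q)D²/SD². Adding site multiplies the SD by √(1 − R²).

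| q | SD of difference in share | 95th percentile of absolute difference | Shift at that percentile, D = 250 / 500 / 1,000 | Power with site (%), SD 2,000, D = 250 / 500 / 1,000 |
|---|---|---|---|---|
| 10% | 6.0 points | 12 points | 30 / 60 / 120 steps | 78.58 / 78.75 / 79.43 |
| 20% | 8.0 points | 16 points | 40 / 80 / 160 steps | 78.63 / 78.93 / 80.14 |
| 50% | 10.1 points | 20 points | 50 / 100 / 200 steps | 78.68 / 79.15 / 81.06 |

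Without site the corresponding power is 78.52%, so the gain is 0.1 to 2.5 points. With SD 2,209, power goes from 70.2% to between 70.2% and 72.4%.

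Worked example for the most favourable corner (q = 50%, D = 1,000, SD 2,000): R² = 0.25 × 1,000²/2,000² = 0.0625. The SE falls from 400 to 400 × √0.9375 = 387, and the 95% half-width from 784 to 759 steps. In the least favourable corner (q = 10%, D = 250), R² = 0.09 × 250²/2,000² = 0.0014.

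**Is validity affected?** Linear models with and without a site term were simulated at q = 20% or 50% and D = 500 or 1,000, SD 2,000, with 8,000 trials per setting. Without site, the mean estimate was within about 7 steps of the truth and type I error was 5.0% to 5.5%; with site, type I error was 5.2% to 5.4%. The simulation error of a 5% rate is √(0.05 × 0.95/8,000) = 0.24 points. Power was 77.7% to 78.2% without site and 77.9% to 80.2% with it. At q = 20%, D = 500 it was 78.2% without and 77.9% with, so at that end the gain is lost in simulation error.

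These calculations treat allocation as unrelated to site. Blocks of two within step bands would, if anything, reduce the imbalance when practice patients enter in runs.

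**The case against.** The best defence is that nothing in the planned inference is wrong. Chance imbalance in an omitted baseline factor is ordinary sampling error, and the standard error already includes it. With central, virtual conduct, site is in effect a referral source, so the usual route to a site effect through local staff and delivery is absent. Differences in activity level are covered by stratification and adjustment on baseline steps. The documents do not show that site predicts step change, and the secondary models could include it. All of this stands, and it limits the point to precision. What it does not answer is that the term costs one degree of freedom and that leaving it to an unnamed secondary adjustment makes its use discretionary.

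Three stronger readings are tempting, and the documents do not support them.

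- A reader might infer that the estimate is biased or the test invalid. Randomization rules that out, and the simulation agrees.
- A reader might infer an urban–rural contrast, or sources chosen to differ. Section 3.2 characterizes only the practice's population; it does not call the health system urban and states no such intention.
- A reader might set the shift against the 1,100-step target and find it large. The proper yardstick is the standard error: even 200 steps is half of 400, and it needs D = 1,000, which is 91% of the planned treatment effect (1,000/1,100).

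**Conclusion.** The point holds as a minor one. Site is absent from both the stratification and the primary model, so a residual site difference in step change stays as unexplained between-patient variance. Bias and type I error are not at stake. Under the assumed ranges the gain from adjustment is about 0.1 to 2.5 points of power. The upper end needs an even split between sources and a site difference nearly as large as the treatment effect; the lower end is practically nil. Both ranges are assumptions, since the documents give no enrolment by source and no expected difference. The case for acting rests on the low price and the value of settling the covariate in advance, not on a large expected benefit.

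**What to change.** In section 5.3, add recruiting site (health system versus private practice) as a fixed effect in the primary step-count model, and likewise in the follow-up and activity-minute models. List it among the predictors of the imputation model, so that imputed days are consistent with the model then fitted to them. Make the change before any comparison by arm. The randomization scheme need not change.

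The cost is a few words of text, one degree of freedom and no new data collection. The gain will be small if few patients come from the practice or if the sources differ little in step change. If the sponsor prefers to leave the primary model as it is, a named sensitivity analysis with site would be an acceptable lesser step.

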4.2. Baseline Questionnaire

After providing informed consent, participants will complete an online questionnaire to confirm eligibility and complete the study surveys.

The baseline survey will consist of the San Diego Claudication Questionnaire and the Walking Impairment Questionnaire to characterize limb symptoms and functional limitations,^{23,24} the Patient-Reported Outcomes Measurement Information System (PROMIS) measures of mobility, pain interference, and satisfaction with social roles and activities,²⁵ and the SF-36 physical functioning scale.²⁶ Patients will also complete several questionnaires to obtain a psychometric profile: the Big Five Inventory survey to evaluate personality characteristics, the Grit Scale to assess perseverance, the Self Efficacy for Exercise Behaviors survey, the PHQ-9 questionnaire to assess mental health state, and the MOS Social Support survey.

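### The symptom subgroups are to be analysed separately with no arm-by-symptom interaction, so the plan gives no valid basis for saying whether the effect differs by symptoms

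*Combined protocol and SAP*

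**What the plan says.** The whole specification of the subgroup analysis is one sentence in section 5.3: "In a subgroup analysis, we will separately analyze subgroups reporting and not reporting exertional lower extremity symptoms". It names no interaction term, no test of heterogeneity and no rule for setting the two results side by side. It also names no instrument or time point for classifying symptoms.

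Nothing else in the document fills the gap. Section 5.3 does look for greater response to gamification, but only in relation to baseline psychometric properties. Its exploratory models relate participant characteristics to good or poor performance, which is not the same as asking whether the arm effect varies with them. Its secondary models adjust for characteristics and do not interact them with arm.

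Two other places bear on the point. Section 4.2 supplies a natural classifier: "The baseline survey will consist of the San Diego Claudication Questionnaire and the Walking Impairment Questionnaire to characterize limb symptoms and functional limitations". Section 4.4 randomises "using a 1:1 allocation and stratifying on baseline step count", so symptom status is not a stratification factor.

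**The concern.** Separate analyses give two arm effects and two p-values. Each p-value tests whether its own effect is zero. Neither tests whether the two effects are equal. The trial is sized for one comparison of 50 against 50, so each subgroup has much less power, and one significant and one non-significant result can easily arise from a uniform effect.

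Readers are likely to look for this contrast. Sections 1.1 and 1.2 stress that patients without classic claudication also have functional limitation and also gain from supervised exercise, and section 3.3.1 does not require symptoms for entry. At stake is a claim that gamification works only in patients with symptoms, or only in those without. The planned analysis could not support such a claim.

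**Working it through.** **Inputs.** From section 5.2: 50 patients per arm, a difference of 1,100 steps, 80% power, alpha 0.05, and SDs of change of about 2,000 (home-based exercise programme) and about 2,400 (gamification). The 1,100 steps match 900 − (−200). Allocation is 1:1 (section 4.4).

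**Assumptions.** A two-sided test (sidedness is not stated), 1:1 allocation within each subgroup, and the subgroup split, which the documents do not give.

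**Step 1: the plan's own figure.** Section 5.2 states: "With 100 patients (50 in each arm), the study will have 80% power to detect an 1100 step difference in change in daily step count". The standard error is SD × √(2/n).
- At SD 2,000 and n = 50 it is 2,000 × √(2/50) = 400. Then 1,100/400 = 2.75, and power ≈ Φ(2.75 − 1.96) = 78.5% (77.7% by noncentral t). This is close to the stated 80%.
- Exactly 80% needs an SD of 1,963 by the normal approximation, or 1,944 by t.
- The root mean square of the two quoted SDs, √((2,000² + 2,400²)/2) = 2,209, gives 69% by t. SD 2,400 gives 62%.

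**Step 2: power within a subgroup.** With a 50/50 split there are 25 per arm in each subgroup. At SD 2,000 the standard error is 2,000 × √(2/25) = 566. Then 1,100/566 = 1.94, and power is 49% by the normal approximation and 47.8% by t.

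**Step 3: chance that exactly one subgroup is significant.** The two subgroups are independent. With subgroup powers p₁ and p₂ and the same true effect in both,

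P(exactly one) = p₁(1 − p₂) + p₂(1 − p₁).

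For SD 2,000 and 50/50 this is 2 × 0.478 × 0.522 = 0.499. The table uses noncentral t and a common effect of 1,100 steps.

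| SD | 50/50 | 60/40 | 70/30 | 80/20 |
|---|---|---|---|---|
| 1,944 | 50% | 51% | 55% | 61% |
| 2,000 | 50% | 51% | 55% | 60% |
| 2,209 | 48% | 49% | 52% | 56% |
| 2,400 | 46% | 47% | 49% | 52% |

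A simulation of 100,000 trials (normal approximation, SD 2,000, 50/50) gave 50.2%.

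**Step 4: dependence on the common effect.** Split 50/50, SD 1,963, by t:

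| Common effect (steps) | Exactly one | Both | Neither |
|---|---|---|---|
| 0 | 9.5% | <1% | 90% |
| 300 | 15% | 1% | 84% |
| 550 | 27% | 3% | 70% |
| 800 | 41% | 9% | 50% |
| 1,100 | 50% | 24% | 26% |
| 1,500 | 37% | 57% | 6% |

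**Step 5: the interaction test.** For SD 2,000 and 50/50, the standard error of the difference between the subgroup effects is √2 × 566 = 800. With identical effects the test rejects 5% of the time by construction (4.9% in the same simulation). For a true between-subgroup difference of 1,100 steps, power is Φ(1,100/800 − 1.96) = Φ(−0.585) = 28%. For 80% power the difference must be about 2.80 × 800 = 2,240 steps.

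**The case against.** The strongest reply is that the plan never says it will compare two p-values or claim a differential effect. Separate estimates with confidence intervals would satisfy the sentence in section 5.3. That is correct. A reader might infer from the figures that the plan raises a 5% error rate to 50%. The documents do not support this: no subgroup comparison is planned, so there is no planned test whose error rate could be raised. The point that stands is narrower. The plan provides no valid comparison, and what it does provide invites an invalid one.

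A reader might also infer that a split result is to be expected under any uniform effect. The second table shows otherwise. At a common effect of 800 steps neither subgroup being significant is more likely (50% against 41%), and at 1,500 steps both being significant is more likely (57% against 37%). The figure of about half belongs to effects near the design value.

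Two further objections stand as limits. The calculation compares mean changes, as the sample size appears to do, whereas the planned analysis is a baseline-adjusted mixed model of repeated daily counts with multiple imputation; adjustment could raise power and missing data could lower it. And the interaction test is itself weak, so a non-significant result could be misread as consistency. That calls for a caution in the report. It does not make separate analyses a better basis for comparison.

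Finally, the symptom subgroups appear neither in the objectives (section 2) nor among the outcomes (section 5.1), so this is a peripheral analysis.

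**Conclusion.** The omission is real: as written, the plan offers no valid basis for saying whether the gamification effect differs by exertional symptoms. If the effect is 1,100 steps in both subgroups, exactly one would reach p < 0.05 about half the time, with a range of 46% to 61% over the SDs and splits tried. With smaller common effects the frequency falls, to 9.5% when there is no effect at all. These figures rest on an assumed split, a two-sided 0.05 threshold and a two-sample comparison of mean change.

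The point is minor. A reader might infer that it weakens the trial's main conclusion, but the primary comparison uses all randomised patients and does not depend on the subgroup analysis.

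**What to change.** Replace the sentence in section 5.3 with a single model in all randomised patients: the primary mixed model plus baseline symptom status and an arm-by-symptom-status interaction. Define symptom status from the baseline San Diego Claudication Questionnaire, which also settles the missing instrument and time point. Report the interaction estimate with its 95% CI, and take both subgroup effects with their CIs from the same model.

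Label the analysis exploratory. State that the interaction test has low power (about 28% for an 1,100-step difference at SD 2,000 and a 50/50 split), so that a non-significant interaction is not evidence of a consistent effect.

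The cost is a few lines of text and the added model terms. No new data are needed.
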